8.1 PRIMARY ANALYSES

Descriptive statistics and graphic displays of all outcome measures will be generated.

The main analysis evaluating the impact of each intervention on the primary study outcome (i.e., the continuous variable change in pain severity and pain interference from baseline to week 8) will use multiple regression models to estimate mean differences between arms along with 95% confidence intervals. The models will include indicator variables to represent study arm. The 2 primary comparisons of interest are between each intervention vs. placebo, i.e., naltrexone vs. placebo; gabapentin vs. placebo, and will adjust for the multiple comparisons using the Hochberg sequential test procedure. We will compare naltrexone vs. gabapentin but these tests will be of secondary interest. If the data are normally distributed, multiple linear regression models will be used. However, if the distribution of change in pain severity is skewed, transformations of the data will be performed (e.g., log transformation). If an appropriate transformation is not identified, a median regression model will be used. Secondary outcomes (e.g., changes in biomarkers, cold pain tolerance) are continuous variables and will be analyzed using the same approach as above.

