2.2 STUDY OUTCOMES

Primary Outcomes: The primary outcome for this study is change in past week pain severity and pain interference (score 0-10) from baseline to week 8. Pain severity and interference will be measured using the Brief Pain Inventory (BPI).

Secondary Outcomes:

Changes in the following secondary outcomes between baseline and week 8 will also be compared among the 3 arms:

- 1) Biomarkers IL-6, IL- β , 1L-10, and TNF- α . Levels of these pro-inflammatory markers will be measured on blood samples collected using commercially available enzyme-linked immunosorbent assay kits (R&D Systems).
- 2) Cold pain tolerance. This will be measured using the cold-pressor test; briefly it is the number of seconds a participant can keep hand submerged in cold water bath.

[figure not shown]
- 3) Percentage of past month heavy drinking days. We will use the Timeline Follow Back to assess drinks per day in the past 30 days. Using a calendar, people provide retrospective estimates of their daily drinking over the past 30 days from the interview date. Definitions of heavy drinking are based on NIAAA guidelines for at-risk drinking (i.e., drinking greater than 14 standard drinks per week/greater than 4 drinks in a day for men; greater than 7 drinks in the past week/greater than 3 drinks in a day for women).
- 4) Measures of HIV control: CD4 cell count and HIV viral load will be measured on participants.

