The purpose of the pilot trial is to generate preliminary data for design of a future larger RCT to demonstrate efficacy. Thus estimation rather than testing is the main objective of this aim. However we provide illustrative power calculations for our primary outcome (change in pain severity) based on prior literature and the number of participants (15 in each arm) we intend to study. It is expected that 45 participants will be enrolled into the study and less than 15% will drop out by 8 weeks. We therefore assume 39 participants (13 per arm) will complete the 8-week follow-up. The following calculations assume 2-sided tests, with an overall significance level of 0.05. For the purposes of power calculations, we consider a simple, conservative setting based on a Bonferroni adjustment for multiple comparisons, although in our analyses we will use the Hochberg sequential correction method, an approach that will result in higher power than the Bonferroni method. To maintain an overall type I error rate of 5%, we assume each of the 2 primary pairwise comparisons (i.e. each intervention vs. placebo) will be conducted at an alpha level of 0.025 for the following power calculations. Based on the 2013 study by Younger, the standard deviation for change in pain severity was 2.9. We expect the standard deviation will be similar in the proposed study and the same for each randomized group. Given this assumption, the minimum detectable difference in change in pain severity between baseline and 8 weeks that the study can detect with 80% power is 3.8 for either of the 2 primary comparisons of interest (i.e., naltrexone vs. placebo; gabapentin vs. placebo), (e.g., -3.0 vs. 0.8 for naltrexone vs. placebo, respectively) using a 2-sided t-test. Because a main goal of the study is estimation of effect sizes for the design of a future study, we also estimate the width of the confidence interval for the mean difference between any two arms for the primary outcome. Our calculations assume 2-sided 95% confidence intervals. Assuming a standard deviation of 2.9 as above, the 95% confidence interval for the mean difference in change in pain severity for either intervention arm vs. placebo would be no wider than 4.7.

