3.2 RANDOMIZATION

After consent and enrollment, participants will be randomly assigned to either low-dose naltrexone, gabapentin, or placebo with a 1:1:1 allocation ratio using permuted blocks to ensure equal numbers in each arm. Participants and research staff will be blinded to randomization arm.

Study medications will be obtained in St. Petersburg and delivered to the study pharmacist at PSMU prior to initiation of recruitment processes. The study pharmacist will deliver a supply of packaged boxes of study medication labeled with the group assignment to the study team.

Following completion of the baseline assessment, the RA will be directed to the electronic randomization screen in REDCap, which, once submitted, automatically assigns the participant to a randomization group. The RA then retrieves the pack of study medication from the identified group, labels the pack with the participant study ID, and enters the group number into REDCap, thus linking the two numbers.

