Return all unused medication to the study site.

DATE OF MANUFACTURE:

SHELF LIFE:

3.4.D. LOST OR STOLEN STUDY MEDICATION

If participants report lost or stolen medication, they will be provided with extra study medication. If participants report losing medication more than once, the study team will be alerted and the case discussed to determine a plan of action.

3.4.E. DISCONTINUATION OF STUDY MEDICATION

If as a result of study testing at week 4, a participant is found to have AST/ALT >10x normal, medications will be discontinued and the participants will be appropriately monitored for resolution of the abnormalities. If a participant has AST/ALT >5x normal as a result of study testing at week 4, participant will be rechecked at their 6-week visit to ensure levels do not increase to the threshold of discontinuation. Any participant with symptoms of acute hepatic failure (jaundice, dark urine) will have AST/ALT checked.

Those who discontinue medication will be followed and analyzed by intention to treat.

Participants found to be pregnant during the study will have their study medication discontinued, but will still be followed-up for the duration of the study. Participants who report pregnancy outside of study

visits will be instructed to immediately discontinue their study medication and requested to come in for a confirmatory urine pregnancy test.

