8. STATISTICAL ANALYSIS

This study will use an intent-to-treat analysis that includes all participants according to their randomized assignment. Descriptive statistics will be calculated for variables at baseline and each follow-up time to assess whether there appear to be any differences across treatment arms.

The main focus of this aim is the assessment the impact of each intervention (naltrexone, gabapentin, or placebo) on the primary study outcome (i.e., the continuous variable change in pain severity from baseline to week 8).

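### Section 8.1 names arm indicators as the only model terms; each outcome's own baseline value should be pre-specified as a covariate

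*Combined protocol and SAP*

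**What the plan says.** Section 2.2 defines the primary outcome: "The primary outcome for this study is change in past week pain severity and pain interference (score 0-10) from baseline to week 8". Section 8.1 models that change with regression and describes the content of the models in one sentence: "The models will include indicator variables to represent study arm". If the data are skewed, the plan moves to a transformation and then to median regression. It extends the method to the other outcomes: "Secondary outcomes (e.g., changes in biomarkers, cold pain tolerance) are continuous variables and will be analyzed using the same approach as above". No section names a baseline value as a covariate. The term multiple regression does not imply one, because two arm indicators already make the model multiple.

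Section 3.2 gives the allocation as "1:1:1 allocation ratio using permuted blocks to ensure equal numbers in each arm" and states no stratification factor. Section 8 plans descriptive statistics at baseline and each follow-up "to assess whether there appear to be any differences across treatment arms", with no action attached. Section 2.7.A makes estimation the main objective, takes a change SD of 2.9 from a cited 2013 study, and sets the number on which precision is based: "We therefore assume 39 participants (13 per arm) will complete the 8-week follow-up".

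**The concern.** In arms of 15, baseline pain can differ by chance. A change score subtracts the whole baseline value, which implies a slope of exactly 1 for week 8 on baseline. If the true slope is below 1, the arm that starts higher appears to improve more than it did. If the slope is above 1, the error runs the other way. With the baseline as a covariate, the data estimate the slope.

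This matters because the arm differences are meant to inform the design of a larger trial. The shift does not show up in the point estimate or interval of the trial that has it. Adding the covariate after the baseline table has been seen would also be harder to defend than naming it now.

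**Working it through.** **Inputs.** From 2.7.A: change SD 2.9, 13 completers per arm, three arms, two-sided 95% intervals. Assumed, because the documents do not give them: baseline SD (sb) of 1.5, 2.0 or 2.5, and baseline to week-8 correlation (r) of 0.3, 0.5 or 0.7.

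**The plan's own figure.** SE of an arm difference = 2.9 × √(2/13) = 1.137. With two-arm degrees of freedom (24), the width is 2 × 2.064 × 1.137 = 4.70, which reproduces the 4.7 stated in 2.7.A. The 8.1 model pools three arms (39 − 3 = 36 df), giving 2 × 2.028 × 1.137 = 4.61. This is the unadjusted comparator.

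**Formulas.** For each sb and r:

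- The week-8 SD (s8) solves s8² − 2·r·sb·s8 + sb² = 2.9².
- Slope of week 8 on baseline = r·s8/sb.
- Shift of the unadjusted contrast per 1-SE baseline imbalance = |slope − 1| × sb × √(2/13).
- Adjusted residual variance = s8²(1 − r²).
- Expected adjusted width = 2 × t(0.975, 35) × √[residual variance × (2/13) × (1 + 1/34)]. The last factor is the average cost of estimating the slope.

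**One cell in full (sb = 2.0, r = 0.3).** s8 = 0.6 + √(0.36 + 4.41) = 2.784. Slope = 0.3 × 2.784/2.0 = 0.418. Shift = 0.582 × 2.0 × 0.392 = 0.46. Residual SD = 2.784 × √0.91 = 2.656. Width = 2 × 2.030 × 2.656 × √(0.1538 × 1.0294) = 4.29.

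**All cells.**

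| r | sb | slope | shift per 1 SE | adjusted width |
|---|---|---|---|---|
| 0.3 | 1.5 | 0.59 | 0.24 | 4.58 |
| 0.3 | 2.0 | 0.42 | 0.46 | 4.29 |
| 0.3 | 2.5 | 0.29 | 0.70 | 3.70 |
| 0.5 | 1.5 | 1.11 | 0.07 | 4.68 |
| 0.5 | 2.0 | 0.83 | 0.13 | 4.65 |
| 0.5 | 2.5 | 0.64 | 0.36 | 4.45 |
| 0.7 | 1.5 | 1.75 | 0.44 | 4.32 |
| 0.7 | 2.0 | 1.37 | 0.29 | 4.53 |
| 0.7 | 2.5 | 1.13 | 0.13 | 4.66 |

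Against 4.61, adjustment is narrower in six cells and at most 0.07 wider in three. A 2-SE imbalance doubles the shift, to 0.13 to 1.40 points.

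**How often.** The two contrasts share the placebo arm, so their baseline differences correlate at 0.5. The chance that at least one exceeds 1 SE is 0.50, and 2 SE is 0.08.

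**Worst case for the covariate.** If baseline explains none of the change, the residual SD stays at 2.9. The width is then 2 × 2.030 × √[8.41 × (2/13) × (1 + 1/34)] = 4.69 on average, and 4.87 in a trial with a 2-SE imbalance (factor 1 + 4/36).

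**Dropout.** The effect of adjustment under missing week-8 data was simulated with a true effect of −2.0, 13.3% missing and 400,000 per arm. Dropout depended on week-4 pain with opposite signs in the two arms (logistic slopes per SD of +1.5 on placebo and −1 on active). There were 18 cells: the nine above, each with a week-4 to week-8 correlation of 0.6 or 0.8. Completer bias was 0.17 to 0.55 points for the change score and 0.11 to 0.60 with baseline adjustment. Adjustment raised the bias in 10 cells and lowered it in 8.

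**The case against.** The strongest reply is that nothing here is an error. The unadjusted change score is unbiased over randomizations and its interval already allows for chance imbalance. The 0.50 and 0.08 probabilities would be the same at any sample size. All of that stands. The argument concerns the estimate in the trial actually run, given the imbalance it happens to have. What sample size changes is the size of an imbalance in points: with 13 per arm, 1 SE is 0.59 to 0.98 points (sb × √(2/13)).

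It can also be said that the gain is unproven, and this too stands. Assuming equal variances at both visits would give a narrowing of 8% to 19%, but the documents do not support that assumption. The r = 0.7 rows imply week-8 SDs of 3.74 to 4.04 on a 0–10 scale, which is high. Leaving them out does not change the ranges, whose extremes come from the r = 0.3 and r = 0.5 rows.

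Three stronger readings are tempting.

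- A reader might infer that the sponsor means to decide on adjustment after seeing the baseline table. Section 8 only describes a comparison, and 8.1 mentions no contingent adjustment. The text is silent on the matter.
- A reader might infer that baseline adjustment also protects against dropout. The simulation shows that it can help or harm.
- Section 8 says "This study will use an intent-to-treat analysis that includes all participants according to their randomized assignment" and 3.4.E says "Those who discontinue medication will be followed and analyzed by intention to treat", while 2.7.A expects 6 of 45 not to complete week 8. A reader might infer that modelling week-4 pain would bring in every randomized participant. It would not: those lost before week 4 still contribute nothing, and the biomarkers, CD4 count and viral load are measured only at baseline and week 8 (3.6.C).

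**Conclusion.** The point holds as a recommended improvement to the specification. Section 8.1 names arm indicators only, and each outcome's own baseline, which is already collected, should be named as a covariate. On the assumed grid, this removes a shift of 0.07 to 0.70 points per 1-SE baseline imbalance, which is at most about 0.6 of the contrast's SE of 1.14. The expected width goes from 4.61 to between 3.70 and 4.68.

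That only arm indicators are named is certain from the text. The size of the benefit is not, because it rests on a baseline SD and a correlation that the documents do not report. The documents do not support calling the planned analysis biased or the covariate a guaranteed gain in precision. Missing week-8 pain is a separate matter that this change does not resolve.

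**What to change.** Add one sentence to 8.1: each model includes the baseline value of the outcome analysed, namely BPI severity in the severity model, BPI interference in the interference model, and each secondary outcome's own baseline in its model. State that the covariate is on the same scale as the outcome if that is transformed, and that it stays in the median-regression fallback. On the untransformed scale, with own baseline in the model, change and week-8 value give the same arm contrast, so the stated primary outcome does not change.

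The cost is one residual degree of freedom (36 to 35) and no new data. If baseline adds little, the interval is about 0.07 to 0.08 wider on average.

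Optionally, and only as a sensitivity analysis beside the primary model, fit a likelihood-based model to week-4 and week-8 BPI (arm by visit, baseline covariate, small-sample degrees of freedom). Participants with week 4 but no week 8 would then contribute. Week-4 BPI is already scheduled in 2.3, 3.1, 3.6.A and the assessment table of section 5.2. The gain is small: 0.2 to 1.0 effective participants per arm if every dropout has week 4, and 0.1 to 0.5 if half do (week-4 to week-8 correlation 0.5 to 0.8). It does not cover participants lost before week 4, outcomes measured only at baseline and week 8, or dropout that is missing not at random.

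### Section 8.1 lets an undefined skewness judgement replace the mean difference in pain change, the only quantity whose precision the protocol plans

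*Combined protocol and SAP*

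**What the plan says.** Section 2.2 defines the primary outcome as "change in past week pain severity and pain interference (score 0-10) from baseline to week 8", measured with the BPI. Section 2.7.A states the purpose: "Thus estimation rather than testing is the main objective of this aim". Its precision statement is that the 95% interval for "the mean difference in change in pain severity for either intervention arm vs. placebo would be no wider than 4.7", and its power example is a two-sided t-test with mean changes of "e.g., -3.0 vs. 0.8 for naltrexone vs. placebo, respectively".

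Section 8.1 opens in the same terms. The main analysis "will use multiple regression models to estimate mean differences between arms along with 95% confidence intervals". It then adds conditions. Linear regression is used if the data are normal. Otherwise, "if the distribution of change in pain severity is skewed, transformations of the data will be performed (e.g., log transformation"). Finally, "If an appropriate transformation is not identified, a median regression model will be used".

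The section ends by extending this to the other endpoints: "Secondary outcomes (e.g., changes in biomarkers, cold pain tolerance) are continuous variables and will be analyzed using the same approach as above".

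**The concern.** The order of the fallbacks is fixed in advance, but the conditions that trigger them are not. Section 8.1 gives no test or cut-off for skewness and no criterion for an acceptable transformation. It does not say whether raw changes or model residuals are judged, whether arms are pooled, or whether the judgement is made blind to arm. The skewness sentence names only pain severity, although pain interference is also part of the primary outcome. One BPI score could therefore be reported as a mean difference and the other as a median difference.

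A raw mean difference, a difference on a transformed scale and a median difference are three different quantities with different precision. The purpose of this pilot is an estimate for planning a larger trial, and its precision is worked out for the first of the three only. Section 8.1 does not commit to reporting that one on every branch.

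The only transformation named does not fit the variable. Change on a 0-10 score runs from -10 to +10, and improvement is negative. The same problem passes to the biomarkers, because the approach is applied to their changes, which also take both signs.

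**Working it through.** **Inputs from Section 2.7.A:** 13 completers per arm, SD of change 2.9, illustrative mean changes -3.0 and 0.8, 95% interval no wider than 4.7.

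**1. The planned width.** Full width = 2 × t(0.975, 24) × SD × √(2/n) = 2 × 2.064 × 2.9 × √(2/13) = 2 × 2.064 × 1.1375 = 4.695. This rounds to the stated 4.7, so the figure is correct, but it belongs to the raw mean difference.

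**2. The same trial on the median branch, normal data, SD 2.9.**
- Large-sample theory: the standard error of a median is √(π/2) = 1.253 times that of a mean, so the width is 4.695 × 1.253 = 5.88.
- Simulation at n = 13 (200,000 samples): the ratio is 1.231, so the width is 4.695 × 1.231 = 5.78.
- The median interval is therefore about 23-25% wider. By the large-sample formula, 19 per arm gives 3.816 × 1.253 = 4.78 and 20 per arm gives 3.713 × 1.253 = 4.65, so about 20 completers per arm would be needed to return to 4.7.

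This is a benchmark for the cost of the switch, not a forecast: data that really are normal should seldom trigger it.

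**3. How much the missing definition matters.** With truly normal data and 39 completers in three arms, judged on arm-centred residuals, the rule would fire in about 16% of trials if skewed meant |skewness| > 0.5. It would fire in about 5% with Shapiro-Wilk p < 0.05, and in about 1% with |skewness| > 1. These cut-offs are assumptions, since the plan gives none.

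**4. The log example.** Assuming normal changes with SD 2.9, the share at or below zero is Φ(3.0/2.9) = 0.85 when the mean is -3.0 and Φ(-0.8/2.9) = 0.39 when the mean is 0.8. A log is undefined for these values unless a constant is added, and the plan states none. The constant is not harmless. With changes held within -10 to +10, adding 10.5, 11, 15 or 20 before taking logs turns the same two distributions into geometric mean ratios of 0.62, 0.65, 0.75 and 0.81.

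**5. Mean against median.** The documents give no shape for the distribution of change, so this part rests on assumptions.
- If treatment only shifts the distribution, there is no gap. With an assumed skewness of -1 and SD 2.9, both differences are 1.10.
- If treatment changes the share of responders, there is a gap. Assume responders fall by 6 points, others by 0.5, and the SD is 2.9 in each arm. For responder shares of 30% vs 10%, 40% vs 20% and 40% vs 10%, the mean differences are 1.10, 1.10 and 1.65. The population median differences are 0.48, 0.44 and 0.71.
- At 13 per arm the average sample median differences in those cases are about 0.67, 0.98 and 1.3, so much of the population gap does not appear at this sample size.

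**The case against.** The strongest defence has three parts.

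First, Section 8.1 begins by committing to mean differences, the fallbacks are ordered, and Sections 8 and 8.1 both call for descriptive statistics. Arm means and SDs of change would normally be among these, and the raw difference with its t interval then follows by arithmetic. This largely stands, and it limits the harm. It does not amount to a commitment that the raw mean difference and its interval will be the primary result.

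Second, the log is only an example, and a log that is undefined for most of one arm could be rejected as unsuitable. That is fair. But the rule then leads straight to median regression, and the plan offers no other transformation and no criterion for choosing one.

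Third, this is a pilot whose power figures are called illustrative. That is true, but a pilot meant for estimation has the most to gain from naming its estimate in advance.

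A reader might also infer that the trial is likely to report an effect about half the true mean difference, or an interval as wide as 7.7 (4.70 × 1.63, from the responder mixtures). The documents do not support that. The mixtures are assumed, the gap shrinks at 13 per arm, and a pure shift gives none. In the SD-2.9 mixtures, skewness-based criteria fire in only about 2-21% of simulated trials. Even when they fire, a transformation is tried before the median.

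**Conclusion.** The point holds as a gap in specification that should be closed. Following Section 8.1 as written can replace the planned estimate with a different and usually less precise one, on a judgement that is not defined, and nothing elsewhere in the document prevents this. Under normality with SD 2.9 and 13 per arm, the cost of ending on the median is an interval of about 5.8-5.9 instead of 4.7. Heavy-tailed symmetric data could reverse that ordering. The inapplicability of a log to pain change follows from the scale itself; the 85% and 39% shares also assume normality.

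The size of any difference between mean and median results cannot be established from the documents. Nor do they support saying that the planned precision is wrong, since it reproduces, or that the mean difference will be lost, since arm means will probably be described. What is missing is the commitment to report the mean difference with its interval whatever the data look like.

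**What to change.** In Section 8.1, replace the sentences from the normality condition through the median regression fallback with a fixed rule. For BPI severity and BPI interference alike, the primary estimate is the difference in mean week-8 score between each active arm and placebo. It comes from linear regression on study arm and the matching baseline BPI score, with t-based 95% intervals, regardless of skewness. With baseline in the model, the arm coefficient is the same whether the outcome is the week-8 score or the change, so the endpoint in Section 2.2 is preserved. Delete the log example for pain change, and keep median regression as a sensitivity analysis only. The Hochberg procedure and the two primary comparisons are unaffected.

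Amend the last sentence of Section 8.1 so that it does not conflict with this rule: where biomarkers or viral load are logged, the baseline and week-8 levels are logged, not the change.

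Baseline adjustment can be separated from the rest. The essential step is to make the raw-scale mean difference primary on every branch.

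The cost is one rewritten paragraph and a little more analysis. Sample size and visits do not change, and baseline and week-8 BPI scores are already collected. The planned width of 4.7 continues to describe the unadjusted mean difference. The downside is that under strong skew the mean may be less typical of a participant than the median, which the sensitivity analysis would show.
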